## **Evaluating the Sleep of an Orthodontic Population Using Emerging Technologies**

Sleep disordered breathing is a highly prevalent indication of airflow limitation. Airflow limitations can occur at the level of the nasopharynx, oropharynx, or hypopharynx. Sleep disordered breathing has a multifactorial etiology, including large fat deposits, a large tongue, consumption of alcohol or sedatives, illness, or excessive relaxation of pharyngeal musculature, among others. These airflow limitations can cause daytime sleepiness, a decrease in productivity, increased blood pressure, or automobile accidents.

Severe airflow limitations can be categorized as either apneas or hypopneas. An apnea involves total breathing cessation for over 10 seconds. A hypopnea involves a partial blockage of airflow for over 10 seconds. These events can culminate in arousal from sleep and gasping for air. The Apnea Hypopnea Index (AHI) is the number of events that occur per hour.

A diagnosis of obstructive sleep apnea involves an AHI score of at least 5. Sleep apnea diagnosis is separated into three categories: mild, moderate, or severe. Mild sleep apnea consists of an AHI score of 5-15 events per hour. Moderate sleep apnea consists of an AHI score of 15-30 events per hour. Severe sleep apnea has an AHI score of over 30 events per hour.

Risk factors for sleep disordered breathing include the male sex, age over 50, BMI >35, a large neck circumference, nasal congestion, diabetes, family history of OSA, and smoking.

Obstructive sleep apnea is highly prevalent, as an estimated 29.4 million adults in the United States have obstructive sleep apnea, though 23.5 million are undiagnosed. This points to the importance of accurate screening tools.

Sleep apnea can be treated using Continuous Positive Airway Pressure (CPAP), oral appliances such as mandibular advancement devices, a hypoglossal nerve stimulation device, lifestyle changes, or surgical intervention such as maxillomandibular advancement, removal of palatine tonsils/adenoids, tongue reduction surgery, or septoplasty.

Untreated sleep disordered breathing can cause many negative effects, including weight gain, cognitive impairment, memory loss, and increased daytime sleepiness. It can also lead to an increased risk of comorbidities, including hypertension, atrial fibrillation, heart attack, stroke, Type 2 diabetes, and depression.

The gold standard for diagnosing obstructive sleep apnea is in-lab polysomnography. In-lab polysomnography records body movement, breathing rate, respiratory effort, nasal airflow, oxygen saturation, blood pressure, heart rate, eye movement, and electroencephalography. The results are interpreted by a sleep technician. Although polysomnography is highly accurate, it is also time-consuming, uncomfortable for the participants, and expensive.

An alternative to in-lab polysomnography is the home sleep apnea test (HSAT). A flow-based HSAT device typically consists of a small wearable monitor with leads, a nasal cannula, chest/abdomen belts, and a pulse oximeter. It records breathing rate, respiratory effort, nasal airflow, oxygen

saturation, and heart rate. It generates a sleep report and can be used for the diagnosis of obstructive sleep apnea. It is a convenient option when compared to polysomnography, but it can be uncomfortable and requires participant compliance. Home sleep apnea tests have lower accuracy than in-lab polysomnography and depend on the participant for proper use.

Questionnaires can also be used to identify obstructive sleep apnea risk factors. There are a variety of questionnaires that can be used, including the NOSE Score Questionnaire, Pittsburgh Sleep Quality Index, STOP-Bang Questionnaire, Insomnia Severity Index, PROMIS Sleep Disturbance Questionnaire, and Epworth Sleepiness Scale.

The STOP-Bang Questionnaire provides a score of “low risk,” “intermediate risk,” or “high risk” for the participant’s risk of an Obstructive Sleep Apnea diagnosis. The participant will check either “yes” or “no” as a response to a series of questions. Each positive response will add one point to the participant’s overall score, which is used for the determination of OSA risk. An overall score of 0 – 2 is “low risk,” a score of 3 – 4 is “intermediate risk,” and a score of 5 or greater is “high risk.”

#### STOP-Bang Questionnaire

*Please answer the following questions by checking “yes” or “no” for each one*

	Yes	No
Snoring (Do you snore loudly?)		
Tiredness (Do you often feel tired, fatigued, or sleepy during the daytime?)		
Observed Apnea (Has anyone observed that you stop breathing, or choke or gasp during your sleep?)		
High Blood Pressure (Do you have or are you being treated for high blood pressure?)		
BMI (Is your body mass index more than 35 kg per m  ?)		
Age (Are you older than 50 years?)		
Neck Circumference (Is your neck circumference greater than 40 cm [15.75 inches]?)		
Gender (Are you male?)		

*Score 1 point for each positive response.*

*Scoring interpretation: 0 to 2 = low risk, 3 or 4 = intermediate risk, ≥ 5 = high risk.*

The NOSE Score Questionnaire involves a series of responses that yield a numerical score representative of the severity of nasal obstruction. The participant provides their responses to a variety of prompts using a ranking system from “Not a problem” (0 points) to “Severe problem” (4 points). The numerical responses are added, then the sum is multiplied by 5, to provide a result of “mild,” “moderate,” “severe,” or “extreme” nasal obstruction.

Over the past one month, how much of a problem were the following conditions for you?

	Not a problem	Very mild problem	Moderate problem	Fairly bad problem	Severe problem
Nasal congestion or stuffiness	0	1	2	3	4
Nasal blockage or obstruction	0	1	2	3	4
Trouble breathing through my nose	0	1	2	3	4
Trouble sleeping	0	1	2	3	4
Unable to get enough air through my nose during exercise or exertion	0	1	2	3	4

NOSE score (multiply your total score x5)

Nasal obstruction severity classification: mild (5-25) | moderate (30-50) | severe (55-75) | extreme (80-100)

The PROMIS Sleep Disturbance Questionnaire evaluates the subject's sleep quality through a series of statements that a subject ranks their agreement from 1 (not at all) through 5 (very much) for the past 7 days. After adding up the numerical values associated with each response, the subject will receive a raw score from 8-40. A conversion chart is used to convert from the raw score to the T Score. A T-Score of <55 is associated with no to slight sleep disturbance, 55.0-59.9 is associated with mild sleep disturbance, 60.0-69.9 is associated with moderate sleep disturbance, and  $\geq 70$  is associated with severe sleep disturbance.

**LEVEL 2—Sleep Disturbance—Adult\***

\*PROMIS—Sleep Disturbance—Short Form

Name: \_\_\_\_\_ Age: \_\_\_\_\_ Sex:  Male  Female Date: \_\_\_\_\_

If the measure is being completed by an informant, what is your relationship with the individual receiving care? \_\_\_\_\_

In a typical week, approximately how much time do you spend with the individual receiving care? \_\_\_\_\_ hours/week

**Instructions to patient:** On the DSM-5 Level 1 cross-cutting questionnaire that you just completed, you indicated that *during the past 2 weeks* you (the individual receiving care) have been bothered by "problems with sleep that affected your sleep quality over all" at a mild or greater level of severity. The questions below ask about these feelings in more detail and especially how often you (the individual receiving care) have been bothered by a list of symptoms ***during the past 7 days***. Please respond to each item by marking (✓ or x) one box per row.

						Clinician Use
In the past SEVEN (7) DAYS....						
	Not at all	A little bit	Somewhat	Quite a bit	Very much	
1. My sleep was restless.	 1	 2	 3	 4	 5	
2. I was satisfied with my sleep.	 5	 4	 3	 2	 1	
3. My sleep was refreshing.	 5	 4	 3	 2	 1	
4. I had difficulty falling asleep.	 1	 2	 3	 4	 5	
In the past SEVEN (7) DAYS....						
	Never	Rarely	Sometimes	Often	Always	
5. I had trouble staying asleep.	 1	 2	 3	 4	 5	
6. I had trouble sleeping.	 1	 2	 3	 4	 5	
7. I got enough sleep.	 5	 4	 3	 2	 1	
In the past SEVEN (7) DAYS....						
	Very Poor	Poor	Fair	Good	Very good	
8. My sleep quality was...	 5	 4	 3	 2	 1	
Total/Partial Raw Score:						
Prorated Total Raw Score:						
T-Score:						

©2008-2012 PROMIS Health Organization (PHO) and PROMIS Cooperative Group.  
This material can be reproduced without permission by clinicians for use with their patients.  
Any other use, including electronic use, requires written permission of the PHO.

Sleep Disturbance 8b Short Form Conversion Table		
Raw Score	T-score	SE*
8	28.9	4.8
9	33.1	3.7
10	35.9	3.3
11	38.0	3.0
12	39.8	2.9
13	41.4	2.8
14	42.9	2.7
15	44.2	2.7
16	45.5	2.6
17	46.7	2.6
18	47.9	2.6
19	49.0	2.6
20	50.1	2.5
21	51.2	2.5
22	52.2	2.5
23	53.3	2.5
24	54.3	2.5
25	55.3	2.5
26	56.3	2.5
27	57.3	2.5
28	58.3	2.5
29	59.4	2.5
30	60.4	2.5
31	61.5	2.5
32	62.6	2.5
33	63.7	2.6
34	64.9	2.6
35	66.1	2.7
36	67.5	2.8
37	69.0	3.0
38	70.8	3.2
39	73.0	3.5
40	76.5	4.4

\*SE = Standard Error on T-score metric

©2008-2012 PROMIS Health Organization (PHO) and PROMIS Cooperative Group.

The Epworth Sleepiness Scale determines the participant's level of daytime sleepiness. It asks the participant to rank their likelihood of falling asleep during a variety of common activities on a scale from 0-3, where 0 is "would never doze," and 3 is "high chance of dozing." After adding up the numerical value of all their responses, the result will determine whether the participant exhibits excessive sleepiness.

Epworth Sleepiness Scale scoring system

	Score
1. Sitting and reading	
2. Watching TV	
3. Sitting in a public place(e.g., theatre or a meeting)	
4. Sitting in a car as a passenger without a break	
5. Lying down to rest	
6. Sitting and talking to someone	
7. Sitting quietly after lunch without alcohol	
8. In a car, while stopped for a few minutes in traffic	
Total score	

(0 = would never doze, 1 = slight chance of dozing, 2 = moderate chance of dozing, 3 = high chance of dozing.)

Total score >10, suggests presence of excessive sleepiness.)

The Insomnia Severity Index (ISI) asks the subject to respond with their level of agreement to a series of prompts related to their sleep habits. The possible responses are on a scale of 0 – 4, where the lower numerical responses indicate little to no presence of insomnia symptoms. After completing the questionnaire, the numerical responses are summed for interpretation. An overall score of 0-7 indicates “no clinically significant insomnia,” a score of 8-14 indicates “subthreshold insomnia,” a score of 15-21 indicates clinical insomnia of moderate severity, and a score of 22-28 is severe clinical insomnia.

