## **Objectives**

To investigate the sleep of the adult orthodontic patient population at the Case Western Reserve University School of Dental Medicine using the NOSE Questionnaire, STOP-Bang Questionnaire, Epworth Sleepiness Scale, Insomnia Severity Index, PROMIS Sleep Disturbance Questionnaire, Sleep Cycle app, and Belun Ring.

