## **Experimental design**

The project will be a descriptive cross-sectional study.

A total of 55 adult participants will be recruited from the Case Western Reserve Orthodontics Clinic, based on the sample size calculation with a power of 80%. Inclusion criteria: current adult patients in the Case Western Reserve Orthodontics Clinic, ages 20-75, willingness to give informed consent

and participate in study, owner of a smartphone, and ability to return the Belun Ring and complete follow-up questionnaire. Exclusion criteria: age <20, currently or with history of taking blood pressure medication, currently undergoing transverse or anterior-posterior orthodontic correction, and currently pregnant or trying to become pregnant.

Participants will provide informed consent and will be instructed on the steps of the study. Demographic information will be collected, including a participant identifier, age of participant, and sex of participant. The use of the Belun Ring will be demonstrated, and they will be instructed on use of the Sleep Cycle app. They will complete the NOSE Score Questionnaire, STOP-Bang Questionnaire, Insomnia Severity Index, PROMIS Sleep Disturbance Questionnaire, and the Epworth Sleepiness Scale (ESS).

Data collected from the STOP-Bang Questionnaire includes positive/negative responses to: snoring, tired, observed, pressure, BMI >35, age over 50, neck size large, male gender, and the resulting OSA risk assessment of low, intermediate, or high.

Data collected from the NOSE Questionnaire includes positive or negative responses to: nasal congestion or stuffiness, nasal blockage or obstruction, trouble breathing through my nose, trouble sleeping, unable to get enough air through my nose during exercise or exertion, and the resulting classification of severity of nasal obstruction (mild, moderate, severe, extreme).

Data collected from the Insomnia Severity Index include difficulty falling or staying asleep, problem with waking up too early, satisfaction level with current sleep pattern, noticeability of subject's sleep problem to others, and amount of distress regarding current sleep habits.

Data collected from the PROMIS Sleep Disturbance Questionnaire includes level of agreement with statements about the subject's ability to fall asleep, quality of sleep, amount of sleep, level of satisfaction with their sleep, ability to stay asleep throughout the night.

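### If used as printed, the PROMIS form tells participants they have reported sleep problems on a DSM-5 questionnaire that the study does not include, a leading prompt that could raise PROMIS scores

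*Combined protocol and SAP*

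**What the plan says.** The background part of the combined protocol and SAP reproduces the PROMIS Sleep Disturbance short form under the heading LEVEL 2—Sleep Disturbance—Adult. Its instructions to the patient open with "On the DSM-5 Level 1 cross-cutting questionnaire that you just completed, you indicated that" and go on to say that the respondent reported sleep problems, at least mild in degree, over the previous two weeks. They then introduce the items as asking about those feelings in more detail, over the past seven days.

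The Objectives section names the study's instruments: "using the NOSE Questionnaire, STOP-Bang Questionnaire, Epworth Sleepiness Scale, Insomnia Severity Index, PROMIS Sleep Disturbance Questionnaire, Sleep Cycle app, and Belun Ring". The Experimental design section gives the enrolment list: "They will complete the NOSE Score Questionnaire, STOP-Bang Questionnaire, Insomnia Severity Index, PROMIS Sleep Disturbance Questionnaire, and the Epworth Sleepiness Scale (ESS". Neither includes a DSM-5 Level 1 measure.

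Participants are clinic patients, not people referred for poor sleep: "Inclusion criteria: current adult patients in the Case Western Reserve Orthodontics Clinic, ages 20-75". The remaining criteria concern consent, smartphone ownership, return of the ring, blood pressure medication, orthodontic treatment and pregnancy.

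On scoring, the paragraph that introduces the form says "the subject will receive a raw score from 8-40" and gives the severity bands, beginning "A T-Score of <55 is associated with no to slight sleep disturbance, 55.0-59.9 is associated with mild sleep disturbance". The raw-to-T table is printed beneath the form as the "Sleep Disturbance 8b Short Form Conversion Table".

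**The concern.** A Level 2 form with this lead-in is written for someone who has already screened positive on a first-stage questionnaire. This study has no first stage and gives PROMIS to everyone it enrols. A participant who sleeps well would read, before rating eight sleep items, that they have already admitted to a sleep problem. That is inaccurate, and it is leading.

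The study is descriptive and covers an orthodontic population not selected for sleep complaints, so the distribution of PROMIS severity is itself a result. All participants would see the same prompt and there is no unprompted group, so the analysis could neither estimate nor remove any effect afterwards.

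**Working it through.** **1. Is the lead-in true of the study's participants?** Set the sections side by side.

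- Form instructions: the respondent has just completed DSM-5 Level 1 and endorsed sleep problems.
- Objectives: five questionnaires, one app, one ring. No DSM-5 Level 1.
- Experimental design, enrolment: the same five questionnaires. No DSM-5 Level 1.
- Experimental design, later procedures: seven nights of ring and app, return visit, Follow-Up Questionnaire. No DSM-5 Level 1.
- Eligibility: no sleep complaint required.
- Anywhere: no statement that the lead-in will be removed, replaced or explained.

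So the lead-in is untrue for participants if the form is used as printed.

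**2. Is the scoring affected?** No. Eight items scored 1 to 5 give a minimum of 8 × 1 = 8 and a maximum of 8 × 5 = 40. This matches the stated raw range and the table's first and last rows. The only question is how people answer.

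**3. How sensitive are the severity bands?** The documents give no size for a prompt effect, so the raw-score shifts below are assumptions. Inputs are the printed conversion table and the bands (below 55, 55.0–59.9, 60.0–69.9, 70 and above). For a shift s at raw score r, the change is T(r + s) − T(r).

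| Assumed shift | Change in T, starting raw 16–32 | Starting raw scores that change band |
|---|---|---|
| 1 | 1.0 to 1.2 | 24, 29, 37 |
| 2 | 2.0 to 2.4 | 23, 24, 28, 29, 36, 37 |
| 4 | 4.0 to 4.9 | 21–24, 26–29, 34–36 |

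The right-hand column covers only scores from which the full shift is possible without passing 40.

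The one-point cases, which need one item to move by one response category:

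- raw 24 to 25: T 54.3 to 55.3, none-to-slight to mild
- raw 29 to 30: T 59.4 to 60.4, mild to moderate
- raw 37 to 38: T 69.0 to 70.8, moderate to severe

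With all 55 planned participants analysed, each person who crosses a cut-off moves a band's percentage by 1/55 = 1.8 percentage points. How many would cross is unknown, because the documents give no expected score distribution.

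**4. Would correlations change?** Let X be the raw score without the prompt, D the shift and Y a device measure.

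- If D is the same constant for everyone, Cov(X + D, Y) = Cov(X, Y) and Var(X + D) = Var(X), so the raw-score correlation is unchanged. T-score correlations would barely move in mid-range, where each raw point is worth 1.0 to 1.2 T.
- If D varies between people, Cov(X + D, Y) = Cov(X, Y) + Cov(D, Y) and Var(X + D) = Var(X) + Var(D) + 2Cov(X, D), so the correlation can change in either direction.

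**5. Which planned analyses use PROMIS?** The comparisons named in the Statistical Analysis Design are STOP-Bang snoring against app audio, snoring against NOSE, STOP-Bang risk against the sensors, and agreement on follow-up between STOP-Bang and the sensors. None uses PROMIS. The referral percentage has no stated PROMIS criterion. PROMIS enters only through the general descriptive statistics and the general correlation of data from different methods.

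**The case against.** **Use as printed is an assumption.** The form sits in the background text, with informant fields and a clinician column that look like a published original. The protocol's own description of PROMIS mentions no DSM-5 step. This stands as a condition on the point. It does not remove it, because the protocol shows no other PROMIS form and announces no edit.

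**Bias is not shown.** A reader might infer that the prompt will inflate scores, more so in good sleepers, and will therefore distort both the severity percentages and the correlations with the devices. The documents do not support that. They give no direction, size or difference between people. A participant who knows they completed no such questionnaire might ignore the sentence or ask staff about it, and a uniform shift would leave correlations essentially intact. This objection stands in full: upward bias is a possibility, not a finding.

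**The shifts have no source.** The table in the working measures how close raw scores lie to cut-offs, not what the prompt does. One raw point at raw 24 is worth 1.0 T, less than the printed standard error of 2.5. That stands, although random error and a shift common to many people are different things, and only the first tends to average out.

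**Similar wording would remain.** The Insomnia Severity Index also speaks of the respondent's insomnia or sleep problem, and it is listed before PROMIS. This stands in part. That form offers a response of none for its symptom items and attributes no earlier answer to the respondent, so it is a weaker prompt.

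**Conclusion.** The mismatch is certain on the page: the form refers to a questionnaire that the study does not include and to a complaint that it does not require. Provided the form is used as printed, participants receive a false and leading instruction that could raise PROMIS scores. The size of any effect cannot be derived from the documents. The most they support is that a single raw point is enough to change the band at raw 24, 29 and 37.

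The stake is modest. It covers the PROMIS severity distribution and general summaries that use PROMIS, and it extends to correlations only if the effect differs between people. The named comparisons and the scoring key are untouched. The correction is still worth making, because PROMIS is part of the stated objective and the change is nearly free.

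**What to change.** Strike the DSM-5 Level 1 sentence and replace the instructions with a neutral one that keeps the recall period, for example: *The questions below ask about your sleep during the past 7 days. Please mark one box in each row.* Leave the eight items, the response values and the conversion table as they are. Do not simply delete everything before the marking instruction, because the sentence stating the 7-day recall would go too and only the column headings would carry it.

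If the form may not be edited, add a cover line asking participants to disregard the DSM-5 sentence. If the printed form has already been used, record which version each participant received so that the two groups can be described separately.

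The cost is a minor ethics notification and confirmation of permission. The notice under the form requires the owner's written permission for any use other than clinicians reproducing it for their patients, so permission should be confirmed for the edited wording.

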## Insomnia Severity Index (ISI)

Name: \_\_\_\_\_ Date: \_\_\_\_\_

1. Please rate the current (i.e., last 2 weeks) **SEVERITY** of your insomnia problem(s).

	None	Mild	Moderate	Severe	Very
Difficulty falling asleep:	0	1	2	3	4
Difficulty staying asleep:	0	1	2	3	4
Problem waking up too early:	0	1	2	3	4

2. How **SATISFIED**/dissatisfied are you with your current sleep pattern?

Very Satisfied	Very Dissatisfied
0	4

3. To what extent do you consider your sleep problem to **INTERFERE** with your daily functioning (e.g. daytime fatigue, ability to function at work/daily chores, concentration, memory, mood, etc.).

Not at all	A Little	Somewhat	Much	Very Much
Interfering				

0      1      2      3      4

4. How **NOTICEABLE** to others do you think your sleeping problem is in terms of impairing the quality of your life?

Not at all	Barely	Somewhat	Much	Very Much
Noticeable				

0      1      2      3      4

5. How **WORRIED**/distressed are you about your current sleep problem?

Not at all	A Little	Somewhat	Much	Very Much

### Guidelines for Scoring/Interpretation:

Add scores for all seven items (1a+1b+1c+ 2+3+4+5) = \_\_\_\_\_

Total score ranges from 0-28

0-7	= No clinically significant insomnia
8-14	= Subthreshold insomnia
15-21	= Clinical insomnia (moderate severity)
22-28	= Clinical insomnia (severe)

Novel wearable technology has been developed that gives information about sleep habits, and some that have the potential to screen for Obstructive Sleep Apnea. Examples of some of these “wearables” include the Oura Smart Ring, Apple Watch, and Belun Ring.

The Belun Ring (formally, Belun Sleep System BLS-100, Belun Technology Co. Ltd., Hong Kong) is a deep learning-facilitated, PPG and accelerometry-based medical-grade wearable, which was recently cleared by the US FDA for the diagnosis of moderate to severe OSA and sleep stage classification in subjects suspicious of OSA (K222579). A recent Belun Ring validation study demonstrated a moderate-to-substantial OSA diagnostic concordance and good overall accuracy in 3-sleep stage classification (REM, non-REM, and wake).

The Belun Ring captures a variety of data points during each night of sleep. One such value is the Respiratory Event Index (REI), which is derived from the total recorded sleep time, heart rate variability, and oxygen saturation changes. The Belun Ring also captures sleep efficiency, which is calculated by dividing the time the participant is asleep by the total time in bed. The Belun Ring's AHI score, "bAHI," has been proven to have a high correlation with a polysomnography-obtained AHI score.

Smart phone apps have also been developed as a new technology used to screen for snoring or sleep apnea. For example, Sleep Cycle, SnoreLab, SleepScore, Drowzle, and Sleep Check Rx are available to the public and produce sleep data after nighttime use for the user's interpretation. The Sleep Cycle app tracks time asleep, stages "Awake, Sleep, and Deep Sleep," sleep regularity, time to bed, time woken up, time in bed, sleep efficiency, heart rate, and time snoring, and also records audio. A score report is generated from each night of sleep, and data are aggregated over time for pattern analysis. Sleep Cycle users also have the ability to add "sleep notes," in which they may record outside factors that may have affected their night of sleep, for example, whether alcohol or caffeine was consumed, if they did a workout that day, if they were feeling sick, etc. Sleep Cycle is available in Apple App Store and Google Play store. The audio recordings are stored in the app, and are automatically deleted after 20 nights.

